Post-Operative Cognitive Dysfunction in Normal Aging Patients Undergoing Elective Orthopedic Surgery

Clinical Study Protocol

NCT: 04267328

Amendment 5 Date: 27 July 2021
Amendment 4 Date: 15 June 2021
Amendment 3 Date: 25 February 2021
Amendment 2 Date: 04 December 2019
Amendment 1 Date: 07 November 2019
Original Protocol Date: 09 September 2019

Sponsor
HealthPartners Center for Memory and Aging
[name]
[name]

This study will be conducted in compliance with the protocol, IND regulations and other applicable regulatory requirements.

Confidential Information

No use or disclosure of this document outside HealthPartners Center for Memory and Aging is permitted without prior written authorization from HealthPartners Center for Memory and Aging.

Participant Contact Project Narrative

1. Summary

Post-operative cognitive dysfunction (POCD) is a common concern for aging patients undergoing elective orthopedic surgery and significantly effects health outcomes. This study aims to evaluate the incidence of and risk factors associated with post-operative cognitive dysfunction in aging patients without prior history for mild cognitive impairment or dementia. Furthermore, we plan to explore neurofilament light (NfL), a blood biomarker of neuronal injury, to better identify patients pre-operatively at greater risk for dementia and therefore, more likely to experience POCD. This project is intended to 1) foster a better understanding of POCD incidence in patients undergoing elective surgery; 2) identify pre and peri-operative risk factors for POCD; and 3) explore the role of biomarkers such as NfL in predicting POCD.

2. Study aims

Primary Aim: Estimate the incidence of post-operative cognitive dysfunction three months after orthopedic surgical intervention.

Secondary Aims:

- Determine pre and peri-operative risk factors associated with development of POCD
- Explore the role of serum neurofilament light (NfL) in predicting risk for development of POCD

3. Background, Rationale, Significance

In neurology clinic, aging patients frequently inquire regarding the risk of cognitive decline following elective orthopedic surgery. These individuals are often faced with the challenging decision of proceeding with surgical intervention while risking potential cognitive decline versus deferring on surgery and enduring the original orthopedic condition justifying the operation.

The term postoperative cognitive dysfunction (POCD) describes a deterioration of cognition that is temporally associated with surgery (Lezak MD Neuropsychological Assessment NY 2004). As opposed to delirium, POCD depends on valid assessments of preoperative and postoperative cognitive function. The underlying etiology of POCD remains unclear. Cerebrovascular disease, cerebral hypoperfusion, genetic susceptibility, alteration in neurotransmitter function, neurohumoral stress, and central nervous system (CNS) inflammatory phenomenon have all been suggested, but the principal suspect has been general anesthesia (Silverstein JH et al Anesthesiology March 2007). However, numerous studies suggest that choice of anesthesia is *not* an important factor in the development of POCD (Wu Reg Anesth Pain Med 2004).

There is an absence of guidelines related to orthopedic surgery and cognitive dysfunction risk to inform the decision-making process for proceeding with surgery in the elderly. The largest trial of POCD was published by anesthesiologists and looked at 1,218 patients aged ≥ 60 at baseline, 1 week, and 3 months post operatively, finding an overall incidence of 25.8% for cognitive dysfunction (Moller JT Lancet 1998). Increasing age, duration of anesthesia, little education, a second operation, postoperative infections, and respiratory complications were risk factors for early postoperative cognitive dysfunction (1 week post-op), but only age was a risk factor for late postoperative cognitive dysfunction (3 months post-op). Limitations to this study include the fact that results were not limited to a certain type of surgery (eg.

orthopedics) and a MMSE of ≥ 24 was used to define normal cognition in this population. Currently, the MMSE is seen as an insensitive screening test in which patients with mild dementia may still score within normal limits ≥ 24 (Lezak MD Neuropsychological Assessment NY 2004).

Since this question of whether POCD is associated with orthopedic surgery has not been extensively investigated in the neurology or orthopaedic literature, we plan to study longitudinal cognitive performance in a cohort of $n=100$ aging patients undergoing elective hip, knee, and shoulder replacement at Regions hospital. Recruitment will take place over a six month period. Consented patients will receive a cognitive battery consisting of standardized measures of attention, learning, memory, processing speed, and mood at baseline and 3 months. In addition to the incidence of post-operative cognitive dysfunction, demographic and clinical variables related to the surgery (eg. age, anaesthesia, medical complications, etc) will be evaluated to identify risk factors. Variables such as cancer, alcohol abuse, and narcotic use are included for evaluation based on the literature suggesting these pre-disposing risk factors may relate to increased risk of POCD. This data will serve to provide valuable information related to risk of cognitive dysfunction following orthopedic surgery, which will not only benefit neurology providers, orthopedic surgeons, but patients who are themselves making informed healthcare decisions, as well.

In addition, we are interested in the utilization of blood biomarkers as predictive factors of POCD. With central nervous system and peripheral nervous system neuronal injury, the concentration of neurofilament light chain (NfL) has been found to increase in cerebrospinal fluid and blood (Olsson B JAMA Neurol 2018). NfL is a subunit of neurofilaments, which are cylindrical proteins exclusively located in the neuronal cytoplasm, conferring structural stability to neurons. In the setting of inflammatory, neurodegenerative, traumatic, or vascular injury to axons, the release of NfL sharply increases, resulting in detectable levels in the blood and CSF (Disanto G Ann Neurol 2017). A variety of neurological conditions that impact the CNS and cognitive result in elevation of blood and CSF levels of NfL; these include HIV associated dementia, amyotrophic lateral sclerosis, Creutzfeldt-Jakob disease, progressive supranuclear palsy, frontotemporal dementia, Lewy body dementia, and Alzheimer's disease (Gaetani L JNNP 2019). Since NfL is a sensitive, but non-specific marker of axonal injury, it may be an effective tool to distinguish aging patients who are at risk of undergoing pre-operative cognitive decline from those who are experiencing normal aging.

4. Approach

a. Study design

This is a prospective, cohort study evaluating cognition at baseline and post-operatively at 3 months in older adults undergoing orthopedic surgery. Any subjects with a history of cognitive impairment or any abnormal cognitive screening result will be excluded from the study.

Findings from the cognitive testing will be compared between baseline and 3 months, and participants with a 1.5 SD decrease in any cognitive domain will be considered to have developed POCD. We will then determine pre and peri-operative risk factors associated with development of POCD. Finally, serum studies for NfL will be drawn during the baseline visit.

b. Population

We will be enrolling patients presenting to Regions orthopedics and TRIA Woodbury with a scheduled surgery. Patients must have one of the following diagnostic codes:

Diagnostic Code
M16.0 Bilateral primary osteoarthritis of hip
M16.12 Unilateral primary osteoarthritis, Left hip
M16.11 Unilateral primary osteoarthritis, Right hip
M17.0 Bilateral primary osteoarthritis of Knee
M17.12 Unilateral primary osteoarthritis, Right knee
M17.11 Unilateral primary osteoarthritis, Right knee
M19.011 primary osteoarthritis, Right shoulder
M19.012 primary osteoarthritis, Left shoulder

In 2018, the orthopedic center conducted 355 primary knee, 283 primary hip, and 76 primary shoulder/reverse shoulder surgeries. Approximately 450 of these were completed by Drs. [name] and [name], from whose patients we will be recruiting. We will also recruit from Drs. [name], [name], and [name]. This excludes non-elective cases, revisions, removals, supplements, and unis. The goal of the study is to recruit n=100 subjects meeting inclusion and exclusion criteria (see below) undergoing elective hip, shoulder, or knee surgery.

i. Inclusion Criteria

1. Age \geq 50 and \leq 90
2. Any patient undergoing elective orthopedic surgery for hip, knee, or shoulder replacement (as defined by the codes above)

ii. Exclusion Criteria

1. History of cognitive impairment of dementia
2. MOCA $<$ 26
3. History of Parkinson's disease, progressive supranuclear palsy, corticobasal degeneration, normal pressure hydrocephalus, Huntington's disease, stroke, seizure disorder, brain tumor, or brain surgery
4. History of surgery requiring anesthesia within the past 3 months
5. Non-English speaking

c. Data collection process

1. *Review of Schedules:* Prior to clinic visits, the orthopedic research assistant will review clinic schedules to identify potential subjects for the next day. Patients presenting for initial visit before elective orthopedic surgery for hip, knee, or shoulder replacement will be pre-screened for this study by orthopedic research assistant based on inclusion/exclusion criteria thorough review of the electronic medical record.
2. *Pre-Surgical Clinic Visits:* During the clinic visit, potentially eligible patients will be given a flyer describing the research study and asked if they are interested in participating. Any questions they have will be addressed. If they are interested, a screening visit will be scheduled and the patient will be given a copy of the informed consent to review at home. If the patient is unsure about participating, they will be sent home with the information and the neuroscience research assistant will follow-up with a phone call in about 3-5 days. There is no phone script for this call. They will be asked if they have further considered participating in the study, any questions they have will be answered,

and an appointment will be scheduled if they are interested. It is not feasible with the orthopedic clinic workflow to complete the MoCA screening during the clinic visit.

3. *Screening & Baseline Research Visits:* Combined screening and baseline visits will be held at the Neuroscience Center (NSC) or remote, via telephone or video (WebEx). Patients will be consented. A research assistant will review the inclusion and exclusion criteria. Patient demographic factors will be entered into case report forms (CRF) and then into REDCap. The patient will undergo a MOCA evaluation to confirm score ≥ 26 if in person, or > 19 for the MOCA Blind if completed remote. Should patients not meet the study threshold for MOCA, they will be counseled regarding their score and available resources. Patients scoring normally on the MOCA will undergo a cognitive battery performed by NSC research assistant. Patients will undergo a blood draw for NfL at NSC regardless of an in person visit or remote. The blood will be sent to a Boston-based laboratory for processing. Results from cognitive battery and blood draw will be entered into REDCap. Patients who complete screening will receive a \$5 gift card. Patients who complete both the screening and baseline visits will receive a \$10 gift card.
4. *Post-Surgical Clinic Visits:* Patients will return to orthopedic clinic for 3 month post-operative visit. This is not a research visit.
5. *Follow-Up Research Visits:* A follow-up visit will be scheduled at NSC or remote for 3 months post-surgery (+/- 2 weeks). The cognitive battery will be administered. If it is desired by the patient, this visit can be coordinated so that it is paired with the orthopedic follow-up appointment, which is close in location. Results from cognitive battery will be entered into RREDCap. Patients who complete the follow-up research visit will receive a \$10 gift card.

d. Intervention, treatments

A cognitive battery will be performed at baseline and then at 3 months post-operatively. A lab for NfL will be drawn during the screening/baseline visit. This is an observational study. There are no treatment interventions for this study.

e. Outcomes/endpoint and other variable definitions, and instruments used

Presence of POCD as determined by neuropsychometric outcome data at baseline and 3 months will be used as the outcome for all three study aims. The neuropsychological tests indicated have strong test-retest reliability. A reduction of 1.5 SD in any neuropsychological test between baseline and 3 months will indicate presence of POCD.

Cognitive Domain	Subtopic	Neuropsychological Test
Global Cognition		MoCA (versions 1 and 2)
Attention	Simple	WAIS-IV Digit Span Forward
	Complex/working mem	WAIS-IV Digit Span Backward
	Complex/working mem	Trails B
Learning/Memory	Immediate	HVLT (versions 1 and 4)

	Delayed	HVLT (versions 1 and 4)
	Psychomotor Speed	Trails A
	Psychomotor Speed	WAIS-IV Digit Symbol Coding
Mood	Anxiety	GAD-7
	Depression	GDS-15

f. Statistical analysis plan

The study population will be described by demographics (e.g. sex, age, race, education status) and baseline health (e.g. vision or hearing impairment, medical history). The appropriate summary measures (mean and standard deviation for continuous variables and frequencies for categorical variables) will be reported. Missing data will be assessed and if a large proportion of data is missing (>10%), we will compare baseline characteristics between subjects to determine if this subpopulation is significantly different. Imputation methods will be considered if differences are found. All statistical analyses will be performed in SAS v9.4 and evaluated at the 0.05 significance level, unless otherwise indicated.

Primary Aim: estimate the incidence of post-operative cognitive dysfunction three months after orthopedic surgical intervention.

This will be defined as a 1.5 SD decline from in any one of the cognitive domains tested baseline to three months. The proportion of patients who develop POCD and a 95% confidence interval will be reported.

Secondary Aim 1: determine pre and peri-operative risk factors associated with development of POCD.

We will be primarily interested in the association between incidences of POCD with the following risk factors:

1. History of delirium
2. Presence of post-operative delirium
3. Regional versus general anesthesia
4. >3 sedating medications added during hospitalization
5. History of prior surgery with general anesthesia

We will fit a logistic regression model with presence of POCD as the outcome of interest and the above risk factors as predictors of interest. We will also include age and gender. As an exploratory analysis, we will fit a model with additional risk factors and use score selection to keep variables with the most impact.

Secondary Aim 2: explore the role of serum neurofilament light (NfL) in predicting risk for development of POCD.

A logistic regression model will be fit with presence of POCD as the outcome of interest and NfL as the predictor of interest to assess the predictive ability of NfL in the development of POCD. We will fit another logistic model that includes NfL and adjusts for the risk factors called out in Secondary Aim 1.

g. Power analysis or statement of precision

In 2018, the orthopaedic center conducted 355 primary knee, 283 primary hip, and 76 primary shoulder/reverse shoulder surgeries. Approximately 450 of these were completed by Drs. [name] and [name], from whose patient populations we will be recruiting. This excludes non-elective cases, revisions, removals, supplements, and unis. The goal of the study is to recruit n=100 subjects. This n was based on both the number of patients we expect to be able to recruit during our timeline, and the estimated study budget. We anticipate the POCD incidence rate will be between 18 and 25% based on previous literature (Moller T et al Lancet 1998). A sample size of 100 produces a two-sided 95% confidence interval with a width equal to 0.157 when the sample proportion is 0.2. This calculation was done using the confidence intervals for one proportion procedure of PASS 2016.

h. Strengths and limitations

Strengths of this study include its focus on post-operative cognitive dysfunction, a topic that is not widely covered in the neurology, orthopedic or anesthesia literature. Furthermore, this study represents a more robust improvement over past investigations of post-operative cognitive dysfunction in normal aging adults in that the Montreal Cognitive Assessment (MOCA) rather than the Mini Mental Status Exam (MMSE) is being used to confirm normal cognition. The MOCA has a 90% sensitivity for mild cognitive impairment whereas the MMSE has an 18% sensitivity for mild cognitive impairment. This will be one of the first studies to evaluate patients exclusively undergoing elective orthopedic surgery whereas prior studies have looked at POCD following a combination of surgical procedures. Finally, this study can be considered pioneering in that it is the first to evaluate the association of blood NfL with risk of post-operative cognitive dysfunction.

Study limitations include the absence of immediate post-operative assessment that may be indicative of a delirium. Our budget allows for a cognitive assessment at baseline and then 3 months in n=100 subjects. We do not have the funding or infrastructure to evaluate patients within their first 3-7 days following surgery. Such information may be helpful in gauging risk for POCD. In addition, we would ideally like to be able to follow cognitive evaluations for 6 and 12 months post-operatively, but likewise do not have funding to evaluate cognition for this period of time while maintaining sufficient numbers of study subjects. Finally, we are unable to include imaging biomarkers of neurodegeneration such as hippocampal atrophy on brain MRI or FDG-hypometabolism of the precuneus/posterior cingulate as we do not have funding to support these diagnostic tests.

5. *Setting/Environment/Organizational feasibility*

The study will be conducted at both the HealthPartners orthopedics clinic as well as the Neuroscience Center. The orthopedics department performs 8-10 total joint surgeries per week with majority of procedures occurring in a population that is older than 50. Potential patients meeting the inclusion and exclusion criteria will be pre-screened at the orthopedics center. The HealthPartners Neuroscience Center has extensive experience with conducting clinical trials and administering neuropsychometric studies. At NSC, patients will undergo cognitive screening and neuropsychometric testing.

[name] is the HealthPartners Neurology Department and Clinical Director of the Center for Memory and Aging; he is serving as the principal investigator of this study. [name] has obtained support from [name], chair of orthopedics and has engaged two orthopedic clinicians, Drs [name] and [name], to include his patients in this investigation.

A common concern expressed by aging patients encountered in both orthopedics and neurology is whether or not undergoing surgery with anesthesia will result in post-operative cognitive decline. Neurology has a department goal of facilitating healthy cognitive aging in the Twin Cities population and limiting environmental exposures that could potentially hasten progression to dementia. Furthermore, the HealthPartners orthopedics department is committed to reducing the risk of post-operative complications, including delirium and progressive cognitive impairment.

6. *Risks and Benefits*

Risks associated with the study include uncovering evidence of undetected cognitive impairment, which may be upsetting to the patient and family. At the same time, this information will be helpful in optimizing patient outcomes. Furthermore, patients will undergo a blood test for NfL that may result in brief discomfort.

Benefits of participating include the opportunity to obtain baseline cognitive testing results, which may better inform patients of current cognitive health. Furthermore, those patients who do end up performing abnormally on the MOCA will be referred for additional diagnostic work-up for dementia.

7. *Data Confidentiality and Privacy*

Data will be stored on a secured server with restricted access to the project folder. Participants will be identified by a study identification number. Secure surveys will be conducted through RedCAP. Data from the CRFs and the cognitive assessment score sheets will be entered into a secure RedCap database. A participant tracking database will also be created in RedCap. Neuroscience research study staff are experienced at building RedCap applications and using them for data entry and participant tracking.

8. *Timeline*

August 2019	Development of cognitive battery workflow
September 2019	Training of research staff in cognitive battery/submission to IRB
October 2019	Education of orthopedic providers re: cognitive assessment
November 2019	Initiate recruitment process
Nov 2019 – Feb 2021	Administration of cognitive battery at baseline and 3 months
March 2021	Data analysis

April 2021	Manuscript preparation/discuss at neurology & orthopedic meetings throughout organization
May 2021	Evaluate inclusion of cognitive battery as a standard clinical initiative in orthopedics
July 2021	Presentation at AAIC Conference
March 2022	AAOS Conference
June 2022	AOA Conference

9. Dissemination/Sharing Results/Integration and Impact

Results from this investigation will be shared during department meetings for neurology and orthopedic surgery, respectively. Furthermore, a presentation will be performed for the Regions HLT meeting as this was a Red-funded grant. Efforts will be made to discuss findings with Park Nicollet neurology and orthopedic departments if it is determined from this study that certain pre-surgical factors are predictive of post-operative cognitive dysfunction.

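### The MoCA score that decides entry appears also to be the baseline for MoCA decline, which biases MoCA change toward decline and adds a modest number of false POCD cases

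*Combined protocol and SAP*

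**What the plan says.** Section 4.c, item 3, sets up a single pre-operative research visit: "Combined screening and baseline visits will be held at the Neuroscience Center (NSC) or remote, via telephone or video (WebEx"). Entry is decided there: "The patient will undergo a MOCA evaluation to confirm score ≥ 26 if in person", "or > 19 for the MOCA Blind if completed remote". Section 4.a gives the same rule in general terms: "Any subjects with a history of cognitive impairment or any abnormal cognitive screening result will be excluded from the study". Patients who pass then take the cognitive battery.

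The instrument table in 4.e lists the MoCA as the only Global Cognition test, as "MoCA (versions 1 and 2"). Two versions fit one administration before surgery and one at 3 months.

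The outcome rule is worded twice. Section 4.e works by test: "A reduction of 1.5 SD in any neuropsychological test between baseline and 3 months will indicate presence of POCD". Section 4.f works by domain: "This will be defined as a 1.5 SD decline from in any one of the cognitive domains tested baseline to three months". Because the MoCA is alone in its domain, it can make a patient a case under either wording.

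Neither section says whose SD is meant. On measurement error the plan offers one sentence, without a coefficient: "The neuropsychological tests indicated have strong test-retest reliability". It describes no second pre-operative MoCA, comparison group, reliable-change index or adjustment for regression to the mean.

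**The concern.** A MoCA score is true level plus error. Requiring a score of at least 26 admits some patients whose true level is lower but whose error was favourable that day. It turns away patients whose error was unfavourable. If change is then measured from the same score, the favourable error is not expected to recur, and the average MoCA falls with no real decline. Alternate versions limit item recall, but they do not remove this selection.

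The gate has a second effect. It confines in-person baseline scores to 26-30 and so shrinks their SD. If the 1.5 SD is taken from the enrolled sample, fewer points are needed to become a case.

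The primary result is one uncontrolled proportion, expected at 18-25%. False MoCA cases would raise it, and the confidence interval would not show this. POCD is also the outcome for both secondary aims.

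**Working it through.** **The plan's own figure.** Section 4.g gives a 95% interval width of 0.157 for n = 100 and p = 0.2. The simple asymptotic interval gives 2 × 1.96 × √(0.2 × 0.8 / 100) = 0.1568, so the figure reproduces. The point here is bias, not that arithmetic.

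**Inputs from the documents.** Entry at MoCA ≥ 26 in person; decline of at least 1.5 SD; n = 100; anticipated incidence 18-25%.

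**Assumptions, not in the documents.** Unselected MoCA mean μ of 26 or 27, SD 2.5, ceiling 30, test-retest reliability r of 0.7 or 0.8, no true change, no practice effect.

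**Model.** T ~ N(μ, r × SD²). Each MoCA is T plus independent error with variance (1 − r) × SD², rounded and capped at 30. Patients enter if the first score X1 is at least 26. A false case has X1 − X2 ≥ 1.5 SD. There were 2,000,000 simulated people per setting.

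**Mean fall.** Ignoring the cap, the expected fall is (1 − r) × (E[X1 | entry] − μ). For μ = 26 and r = 0.7, entry after rounding means an unrounded score of at least 25.5, i.e. z ≥ −0.2. So E[X1 | entry] − μ = 2.5 × 0.391 / 0.579 = 1.69, and the fall is 0.3 × 1.69 = 0.51 points. The simulation with the cap gives 0.53. Over the four settings the fall is about 0.25 to 0.53 points.

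**SD.** The gate shrinks the observed SD from about 2.3-2.4 to about 1.4. Then 1.5 × 1.4 = 2.1, so a 3-point loss makes a case. With the unselected SD, 1.5 × 2.5 = 3.75, so a 4-point loss is needed.

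**Separating the sources.** In the same enrolled patients and at the same cut, I compared the entry score as baseline with a second baseline MoCA not used for entry. The difference is the part due to reuse.

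| μ, r | Enrolled SD: entry score / separate baseline | Due to reuse (points) | Unselected SD: entry score / separate baseline | Due to reuse (points) |
|---|---|---|---|---|
| 26, 0.7 | 13.1% / 8.7% | 4.4 | 4.8% / 2.9% | 1.9 |
| 27, 0.7 | 10.5% / 7.8% | 2.7 | 3.6% / 2.5% | 1.1 |
| 26, 0.8 | 7.5% / 5.0% | 2.4-2.5 | 1.8% / 1.1% | 0.7 |
| 27, 0.8 | 6.0% / 4.5% | 1.4-1.5 | 1.4% / 1.0% | 0.4 |

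Where two values are shown, runs differ by rounding. As a check on direction, gains of the same size occur in 2.3-4.0% (enrolled SD) and under 1% (unselected SD).

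**Sensitivity.**
- Practice gain, enrolled SD: 0.5 point lowers the totals to about 3.0-8.2%, and 1 point to 1.4-4.8%.
- Reliability 0.90: totals are under 2% (enrolled SD) or about 0.1% (unselected SD).
- Wider grid (mean 25-27, SD 2.0-3.0, reliability 0.60-0.90): the part due to reuse runs from about 0 to 14 percentage points.

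**Who the false cases are (enrolled SD).** By observed score, 26 has the lowest rate: with μ = 26 and r = 0.7 it is about 8% at 26, 11% at 27, 15% at 28, 19% at 29 and 18% at 30. By true level the pattern reverses: 19-30% of enrolled patients truly below 25.5 are flagged, against 2-5% of those above 28.5. Patients truly below 25.5 are about 7-14% of those enrolled and 21-32% of the false cases.

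**The case against.** The strongest reply has four parts.

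- **Reuse of the score is inferred.** The plan never says that the entry MoCA is the baseline MoCA. This stands as a limit. One combined visit and two versions make it the natural reading, but the sponsor should confirm it.
- **Most of the total is not selection.** A reader might take the 13% as about 13 false cases per 100 caused by the gate. The calculation does not support that, since a separate baseline at the same cut still gives 8.7%. Some of these patients might also qualify on another test, so even the totals are not net additions to the incidence.
- **Every MoCA parameter is assumed, and practice works the other way.** This stands. The plan calls reliability strong, and at 0.90 the problem nearly vanishes. But it gives neither a coefficient nor the source of the SD, so it does not show that the favourable case applies.
- **The bias may not be confined to the MoCA.** A generally good day would raise the other tests at the same visit too. The model assumes independent errors, so this was not examined, and leaving out the MoCA would not cure it.

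Two further inferences are tempting. One is that false cases gather among patients scoring near 26. The simulation shows the opposite by observed score; the excess is among patients whose true level is below the gate. The other is that the risk-factor and NfL models are therefore distorted. That is plausible if a predictor tracks true cognitive level, but it was not quantified. The remote MoCA Blind threshold raises the same issue and was not simulated.

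**Conclusion.** The concern holds at modest size. If the entry MoCA is the baseline MoCA, the plan as written biases MoCA change toward decline and corrects for it nowhere. Under the central assumptions, reuse of the score adds about 1.4-4.4 false MoCA cases per 100 with the enrolled-sample SD, or 0.4-1.9 with the unselected SD. These sit within totals of 6-13% and 1.4-4.8%. The totals can be set beside an anticipated incidence of 18-25% and a planned interval 15.7 points wide, but they are gross of overlap with other tests. The direction of the selection effect needs only imperfect reliability; its size cannot be fixed from the documents and may be close to nil. Confidence is moderate. This merits a cheap change of wording, and it does not invalidate the primary aim.

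**What to change.** In 4.e and 4.f, state that the MoCA is used for eligibility and description only and is not among the tests or domains that define POCD in the primary analysis. The definition then rests on Digit Span, Trails, HVLT and Digit Symbol Coding as its cognitive tests, none of which is an entry criterion. Report the 3-month MoCA change descriptively, and give a sensitivity incidence that includes the MoCA. State also whether the entry MoCA is the baseline value, and which SD the 1.5 SD rule uses.

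The cost is a sentence or so in each section, with no new visits or data. The downside is that a patient who declines only on the MoCA is counted only in the sensitivity analysis. The change removes MoCA-driven false cases from the primary proportion; it does not remove ordinary retest error in the remaining tests.

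### Secondary Aims 1 and 2 analyse only the yes/no POCD label; a prespecified continuous-change model alongside it would recover power for modest, widespread decline

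*Combined protocol and SAP*

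**What the plan says.** Section 4.e makes presence of POCD the outcome throughout: it "will be used as the outcome for all three study aims". The label is a threshold rule: "A reduction of 1.5 SD in any neuropsychological test between baseline and 3 months will indicate presence of POCD". Section 4.a words the same rule by domain: "participants with a 1.5 SD decrease in any cognitive domain will be considered to have developed POCD".

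The underlying scores exist. Section 4.d states: "A cognitive battery will be performed at baseline and then at 3 months post-operatively". The table in 4.e lists eight cognitive measures (MoCA, Digit Span Forward and Backward, Trails A and B, HVLT immediate and delayed, Digit Symbol Coding) and two mood scales.

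For Secondary Aim 1, section 4.f says: "We will fit a logistic regression model with presence of POCD as the outcome of interest and the above risk factors as predictors of interest", with age and gender added. For Secondary Aim 2: "A logistic regression model will be fit with presence of POCD as the outcome of interest and NfL as the predictor of interest", followed by a second logistic model that adds the Aim 1 risk factors. No model of continuous change is specified. Section 4.a does mention comparing baseline with 3-month findings, but only as the step that produces the label.

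Section 4.g bases n=100 on recruitment and budget and anticipates 18–25% incidence. Its one calculation is the confidence interval width for that incidence. No detectable effect is given for any risk factor or for NfL.

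**The concern.** A yes/no label is the right summary for an incidence. It is a coarse outcome for finding associations: a patient who falls 1.4 SD on every test is counted the same as one who improves on every test. With 18–25 events expected in 100 patients, the two secondary aims rest on few events, while the graded data behind the label go unused.

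Sample size cannot easily be raised, because it was fixed by recruitment and budget. The sponsor also hopes the results will support a larger grant (section 9). A null result for NfL or anaesthesia type that reflects the coarse outcome could mislead that next step.

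**Working it through.** **Inputs from the document.** n=100; incidence 18–25%; significance level 0.05 (taken as two-sided); eight cognitive measures.

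**Assumed, because the document gives no figure.** Exposure prevalence, effect sizes, between-test correlation, normally distributed changes, no dropout. All power figures are unadjusted.

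**Step 1: the plan's own figure.** Width = 2 × 1.96 × √(0.2 × 0.8/100) = 0.1568, which matches the stated 0.157.

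**Step 2: information kept by one cut.** Relative efficiency = φ(z_p)²/[p(1−p)].
- p=0.18: 0.466
- p=0.20: 0.490
- p=0.25: 0.539

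So 100 patients act like about 47, 49 or 54, a loss of 53%, 51% or 46%.

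**Step 3: a binary exposure and the any-of-eight rule.** The cutoff was set to give 20% POCD, either overall or in the unexposed. The SD is that of the change score. Label power comes from simulation with a Wald or two-proportion test; it moves by several points with the calibration and the test, hence the ranges.

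The mean-change power can be checked in closed form. The mean of eight changes has SD √[(1+7ρ)/8], and power ≈ Φ(δ√[nπ(1−π)] − 1.96), where δ is the average shift divided by that SD and π is the proportion exposed. For 0.3 SD on all tests:
- ρ=0.1, π=0.5: δ = 0.3/0.461 = 0.651; 0.651 × 5 = 3.25; power 90%
- ρ=0.3, π=0.5: δ = 0.3/0.622 = 0.482; 0.482 × 5 = 2.41; power 67%
- ρ=0.5, π=0.5: δ = 0.3/0.75 = 0.40; 0.40 × 5 = 2.00; power 52%
- ρ=0.3, π=0.05: 0.482 × √4.75 = 1.05; power 18%

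| Exposed | Correlation | Shift | POCD label | Mean change |
|---|---|---|---|---|
| 50% | 0.1–0.3 | 0.3 SD, all eight | 25–38% | 66–91% |
| 50% | 0.5 | 0.3 SD, all eight | about 26% | about 51% |
| 10% | 0.3 | 0.3 SD, all eight | 15–20% | about 30% |
| 5% | 0.3 | 0.3 SD, all eight | about 15% | about 18% |
| 50% | 0.1–0.3 | 0.6 SD, two tests | 16–19% | 22–37% |
| 10% | 0.3 | 0.6 SD, two tests | 14% | 11% |
| 50% | 0.1–0.3 | 0.8 SD, one test | about 14% | 11–19% |

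**Step 4: a continuous predictor such as NfL.** The odds ratio per SD detectable with 80% power is exp[(1.960+0.842)/√(np(1−p))]. At p=0.20 this is exp(2.802/4) = 2.01; at 18% and 25% it is 2.07 and 1.91.

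For a single normal change score cut at 20%, by the correlation r between predictor and change:
- r=0.20: 29% (label) against 52% (continuous)
- r=0.30: 57% against 87%
- r=0.40: 82% against 99%

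For the any-of-eight label, with a predictor that moves every test by 0.18 SD per SD, power is 39% (label) against 89% (mean change) at correlation 0.2, and 34% against 74% at correlation 0.4.

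**Step 5: what n=100 cannot do on any scale.** The detectable difference on a continuous outcome is 2.802/√[100π(1−π)]: 0.56 SD at 50% exposed, 0.93 SD at 10% and 1.29 SD at 5%.

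**The case against.** The strongest reply is that the aims ask about development of POCD, and a logistic model of POCD answers exactly that. A shift in mean score that carries nobody across the threshold is not POCD. Making a composite the main analysis would replace the question. This stands, and it is why the composite belongs beside the logistic models and not in front of them.

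Second, a reader might infer that risk-factor and NfL effects are largely undetectable with the label. The figures do not support that: an unadjusted NfL odds ratio near 2 per SD has about 80% power. The problem is with modest effects.

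Third, a reader might put the low power down to dichotomising alone. Step 5 shows otherwise. History of delirium and post-operative delirium may be uncommon (an assumption; no prevalence is given), and for rare factors n=100 is the main limit whichever outcome is used.

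Fourth, the composite is not always better. POCD is defined by decline in any one test or domain, so focal decline is part of its target, and there the advantage shrinks or reverses.

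Finally, Secondary Aim 2 is exploratory and no power is claimed for either secondary aim. That lowers the weight of the point. It does not explain why data already collected should go unused.

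**Conclusion.** The point holds as a cheap improvement, not as an error in the plan; the primary incidence is unaffected. Confining the secondary aims to the label gives up about 46–53% of the information in a single normal change score at the anticipated incidence. For a modest decline spread over all eight measures with a common exposure, the label has roughly one quarter to somewhat over one third power, where a mean change has two thirds to nine tenths; at correlation 0.5 the mean change still has about twice the power.

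The information figure rests on normality and the plan's own incidence. The power figures rest on assumed prevalence, correlation and pattern of effect, and on a cutoff placed to give 20% POCD, not on the 1.5 SD rule itself. The documents do not support the further conclusions that the logistic models are wrong or that they should be demoted.

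The difference between the per-test wording in 4.e and the per-domain wording in 4.a and 4.f is a separate matter. It affects the incidence and should be reconciled.

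**What to change.** Keep POCD yes/no for the primary incidence, and keep the logistic POCD models for both secondary aims as stated. Prespecify alongside them, before any analysis, a linear regression for each secondary aim with:

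- **Outcome:** the composite 3-month cognitive score, the mean of the cognitive z-scores, each standardised to the baseline sample SD and signed so that higher is better.
- **Excluded:** GAD-7 and GDS-15. Also leave MoCA out where its version differs between visits or patients; section 4.c allows remote visits and uses the MoCA Blind for remote screening.
- **Covariates:** the baseline composite, plus the same predictors as the matching logistic model.
- **Role:** a supporting analysis of graded decline, reported whatever its result.

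The cost is a paragraph in section 4.f, a short scoring specification and one more analysis per aim, with no new patients, visits or assays. The downsides are that effects are in SD units and not odds of POCD, and that a decline confined to one test is diluted in the composite.
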